6.4 STUDY INTERVENTION COMPLIANCE

Because the study medication will be ordered in Epic and administered by the clinical bedside nurse, medication administration will be documented in Epic per usual nursing policies. Compliance will be assessed via review of the electronic health record documentation.

6.5 CONCOMITANT THERAPY

Intraoperatively, enrolled participants should not receive open-label ketamine. Otherwise, all components of the anesthetic care plan will be at the discretion of the attending anesthesiologist.

Postoperatively, enrolled participants should not receive open-label ketamine. During the study medication infusion, concurrent infusions of propofol, midazolam, or other sedative agents with GABA receptor activity will not be permitted. Concurrent dexmedetomidine is permitted. During the study medication infusion, administration of benzodiazepines or gabapentin will not be permitted. All other components of postoperative care will occur as directed by the clinical team.

Medications administered to the patient will be retrieved by the research team from the electronic health record. In particular, administrations of the following medication classes between 05:00am on the day of the study medication infusion and 06:00am on post-infusion day 2 will be retrieved:

- Benzodiazepines
- Anticonvulsants
- Alpha agonists (dexmedetomidine, clonidine)
- Hypnotic agents
- Antihypertensive agents
- Antiarrhythmic agents

Administrations of the following medication classes between 06:00am on the day of the study medication infusion and 06:00am on post-infusion day 7 will be retrieved:

- Opioid analgesics
- Non-opioid analgesics
- Antiemetics

6.5.1 RESCUE MEDICINE

Not applicable

7 STUDY INTERVENTION DISCONTINUATION AND PARTICIPANT DISCONTINUATION/WITHDRAWAL

7.1 DISCONTINUATION OF STUDY INTERVENTION

Infusion of the study medication may be halted if the patient experiences sedation to a Richmond Agitation and Sedation Scale (RASS) score of -2 (light sedation: briefly awakens <10 sec with eye contact to voice) or lower. Once the patient has returned to a RASS of -1 (drowsy: sustained awakening >10 sec with eye contact to voice) or greater, the study medication may be restarted as noted below:

- If the medication was halted during the bolus loading dose, then the bolus will not be resumed. After recovery to RASS \geq -1, the continuous infusion will be started at 0.3 mg/kg/h ketamine or 0.06 mL/kg/h normal saline.

- If the medication was halted during the continuous infusion of 0.3 mg/kg/h ketamine or 0.06 mL/kg/h normal saline, then the infusion will be restarted at 0.2 mg/kg/h ketamine or 0.04 mL/kg/h normal saline after recovery to RASS \geq -1.
- If the medication was halted during an infusion at 0.2 mg/kg/h ketamine or 0.04 mL/kg/h normal saline, then the infusion will be restarted at 0.15 mg/kg/h ketamine or 0.03 mL/kg/h normal saline after recovery to RASS \geq -1.
- If the medication was halted during an infusion at 0.15 mg/kg/h ketamine or 0.03 mL/kg/h normal saline, then the infusion will not be restarted.

Discontinuation of the study medication as described in this section may result in inadvertent unblinding of the patient and clinical staff. We will assess for inadvertent unblinding as described in section 6.3.

If 3 patients require the study medication to be halted, then the principal investigator will consider revising the dosages and/or infusion rates listed in section 6.1.2.

If the clinical team feels it is necessary to halt the study medication for a reason other than RASS $<$ -1, this will be discussed with the principal investigator or a qualified designee.

Discontinuation of the study medication does not mean discontinuation from the study, and remaining study procedures should be completed as indicated by the study protocol. If a clinically significant finding is identified (including, but not limited to changes from baseline) after enrollment, the investigator or qualified designee will determine if any change in participant management is needed. Any new clinically relevant finding will be reported as an adverse event (AE).

7.2 PARTICIPANT DISCONTINUATION/WITHDRAWAL FROM THE STUDY

Participants are free to withdraw from participation in the study at any time upon request.

An investigator may discontinue or withdraw a participant from the study for the following reasons:

- If any clinical adverse event (AE), laboratory abnormality, or other medical condition or situation occurs such that continued participation in the study would not be in the best interest of the participant
- If the participant meets an exclusion criterion (either newly developed or not previously recognized) that precludes further study participation

The reason for participant discontinuation or withdrawal from the study will be recorded on the Case Report Form (CRF). Subjects who sign the informed consent form and are randomized but do not receive the study intervention may be replaced. Subjects who sign the informed consent form, and are randomized and receive the study intervention, and subsequently withdraw, or are withdrawn or discontinued from the study, will not be replaced.

7.3 LOST TO FOLLOW-UP

A participant will be considered lost to follow-up if he or she is unable to be contacted by the study site staff after hospital discharge for three consecutive follow-up assessments.

For each post-discharge follow-up assessment, the following actions will be taken if the patient is unable to be contacted:

- Before a participant is deemed lost to follow-up, the investigator or designee will make every effort to regain contact with the participant (where possible, 3 telephone calls and, if necessary, a certified letter to the participant's last known mailing address or local equivalent methods). These contact attempts should be documented in the participant's study file.
- Should the participant continue to be unreachable, he or she will be considered to have withdrawn from the study with a primary reason of lost to follow-up.

8 STUDY ASSESSMENTS AND PROCEDURES

8.1 EFFICACY ASSESSMENTS

Depressive Symptom Measurement

Depressive symptoms will be measured using the Montgomery-Asberg Depression Rating Scale (MADRS) preoperatively and on post-infusion days 1, 2, 4, 7, and 14. The MADRS rates the severity of 10 depressive symptoms based on a targeted clinical interview, yielding a total score 0 (no symptoms) and 60 (severe symptoms).^{49,50} The scale has been found to correlate highly with a global clinician assessment (Pearson correlation = 0.71)⁵¹ and to have high inter-rater reliability.⁴⁹ The MADRS has been modified to assess symptoms over the previous day rather than the previous week.^{36,37} This modified version will be used on the post-infusion days.

The MADRS will be administered by a trained research team member. Post-infusion assessments will be conducted between 07:00am and 12:00pm approximately on the specified days. The time of day for the preoperative assessment will be variable, depending on the time of the patient's CPAP appointment or in-hospital visit. If the patient is discharged from the hospital before the day of the final study assessment, the MADRS will be conducted over the telephone.

Concurrent with each MADRS assessment, the research team member will use the Clinical Global Impression (CGI) to rate the overall severity of the patient's mental illness.⁵² At each postoperative follow-up, the CGI will also be used to rate the overall level of improvement compared to the previous assessment.

Concurrent with each MADRS assessment, self-reported depressive symptoms will be collected using the Quick Inventory of Depressive Symptomatology (QIDS).⁵³

The MADRS includes questions about suicidal ideation. If the patient reports any suicidal ideation, then the Suicide Risk Management Protocol will be initiated. This includes a structured assessment allowing stratification of the risk for self-harm, notification of the principal investigator, and (if risk is moderate or high) notification of an on-call psychiatrist.

Electroencephalogram (EEG) Measurement

EEG will be captured using the Dreem headband (DREEM, Rhythm, New York, NY), a consumer-grade wireless device using dry electrodes. The device uses five EEG channels (F7, F8, FpZ, O1, O2), accelerometry, and pulse oximetry. It samples EEG electrode potentials at a rate of 250 Hz and applies a 0.4-30 Hz bandpass filter.

At the baseline visit, the research team member will teach the participant how to use the Dreem headband for data collection. If the participant is recruited in the CPAP clinic, then the participant will take the Dreem headband home with them. They will be instructed to wear the headband and activate data collection while sleeping for one night. They will bring the headband back to the hospital with them

on the day of surgery. If the participant is recruited in the hospital, then the participant will wear the headband and activate data collection while sleeping the night following enrollment. The headband will be retrieved the following day.

Additional data collection using the Dreem headband will occur in preoperative holding, during the study medication infusion, the night following the study medication infusion, and the night following post-infusion day 1.

Postoperative Pain

Pain will be measured at the baseline visit and on post-infusion days 1, 2, 4, 7, and 14 using the visual analog scale. The participant will rate their pain at rest, when taking a deep breath, and with movement.

If the participant is discharged from the hospital before the day of the final study assessment, pain will be assessed over the telephone using an 11-point numeric rating scale at each remaining study time point. Pain will be rated at rest, when taking a deep breath, and with movement.

Postoperative Delirium

Delirium is assessed routinely by the ICU nurses using the Confusion Assessment Method for the ICU (CAM-ICU) once per shift. CAM-ICU scores between the day of the infusion and post-infusion day 5 will be retrieved from the electronic health record.

8.2 SAFETY AND OTHER ASSESSMENTS

Psychotomimetic Side Effects

Psychotomimetic effects will be quantified using the Brief Psychiatric Rating Scale (BPRS) four-item positive symptom subscale^{36,54} and using the modified 6-item Clinical Administered Dissociative State Scale (CADSS-6).⁵⁵ The BPRS four-item subscale yields a score between 4 (no symptoms) and 28 (extremely severe). The CADSS-6 yields a score between 0 (no symptoms) and 24 (severe symptoms). Both scales will be administered by a research team member midway through the study medication infusion (approximately 1-2 hours after the start of the bolus loading dose).

Clinical and Adverse Events Checklist

Additional side effects of ketamine will be detected using the Clinical and Adverse Events Checklist.⁵⁶ This checklist will be administered by a research team member midway through the study medication infusion (approximately 1-2 hours after the start of the bolus loading dose). The checklist will be repeated on post-infusion day 14 to monitor for resolution of any side effects.

Level of Sedation

Although the doses of ketamine used in this study are not expected to produce clinically significant sedation, patients will be monitored for sedation using the Richmond Agitation and Sedation Scale (RASS). RASS assessments will be conducted by the clinical bedside nurse per standard nursing protocols of the ICU. The nurse will also be asked to perform one extra RASS assessment at the end of the 10-minute bolus loading dose. If the RASS score is ever -2 or lower, the study medication will be held according to the protocol described in section 7.1.

Vital Signs during Study Medication Infusion

During the infusion, participants will receive vital sign monitoring per intensive care unit standard of care. This will include continuous telemetry, continuous pulse oximetry, and either intermittent

noninvasive blood pressure (at least hourly) or continuous invasive blood pressure (if an arterial catheter is present). Vital signs will be documented in the electronic health record by the clinical bedside nurse per unit standard of care. The research team will retrieve vital signs from the electronic health record.

Safety events will include significant hypertension during the infusion, defined as systolic blood pressure > 180 mmHg or the administration of an antihypertensive medication that is not one of the patient's home medications. Another safety event will be tachycardia, defined as heart rate > 100 beats per minute, during the infusion.

Nausea and Vomiting

At each post-infusion study visit, participants will be asked if they have experienced nausea or vomiting in the past 24 hours. If present, the patient will be asked to classify the event as mild, moderate, or severe. In addition, the electronic medical record will be reviewed for administration of antiemetic medication.

Baseline Factors Potentially Related to Depression

At the time of enrollment, the patient will complete several surveys evaluating factors that may be related to their depressive history or that may predict treatment responsiveness. These surveys will include the Generalized Anxiety Disorder 7-item scale (GAD-7),⁵⁷ the Alcohol Use Disorders Identification Test (AUDIT),⁵⁸ the Drug Abuse Screening Test (DAST-10),⁵⁹ and the Childhood Trauma Questionnaire (CTQ).⁶⁰

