4.3 JUSTIFICATION FOR DOSE

In the intervention group, the dosing regimen has been designed to quickly achieve the desired blood level of ketamine of 225 ng/mL and then maintain that level throughout the infusion. A desired blood level of 225 ng/mL has been selected because this is half of the serum concentration obtained during steady state for a 96-hour infusion.³⁶ This level is also only slightly higher than the peak blood level obtained after patients receive a 0.5 mg/kg bolus dose delivered over 40 minutes, first described by Krystal in 1994⁴⁷ and used frequently in subsequent studies. Such a dosing approach would address the question of clinical utility in prolonging the length of anticipated NMDA receptor blockade from several minutes to 8 hours.

Loading Dose – The alpha distribution half-life for ketamine is about 10 minutes. A load over 10 minutes instead of an immediate bolus should be feasible in that this would lessen the likelihood of significant sedation, and it would provide time to detect the rare instances of more moderate sedation with the load. Thus, this loading approach carries minimal risk of unintended over-sedation. Also given the beta half-life of about 2.3 hours, there would not be substantial loss of ketamine during the 10-minute load.

The risk of over-sedation may be larger in patients with elevated body mass index (BMI), due to a higher peak concentration prior to redistribution throughout all tissue (including the excess adipose). To reduce the peak concentration without decreasing the expected plasma concentration at the end of the bolus load, the bolus load duration will be increased to 20 minutes in patient with BMI > 40.

We want to load the patient with an amount equal to 100% of the desired steady state. Thus, the loading dose is equal to the product of the volume of distribution and the desired plasma concentration. Per Wagner and O'Hara,⁴⁸ the volume of distribution of ketamine is 2.4 L/kg. As noted above, the desired plasma concentration is 225 ng/mL, which is equal to 0.225 mg/L. Therefore, the loading dose will be

$$2.4 \frac{\text{L}}{\text{kg}} \times 0.225 \frac{\text{mg}}{\text{L}} = 0.54 \frac{\text{mg}}{\text{kg}}$$

Thus, we will plan to load with a bolus of 0.5 mg/kg over 10 minutes (or over 20 minutes if BMI > 40).

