6.1.2 DOSING AND ADMINISTRATION

The study intervention consists of a bolus loading dose followed by a continuous infusion. For patients in the intervention group, the bolus loading dose will consist of ketamine 0.5 mg/kg administered intravenously over 10 minutes (or over 20 minutes if BMI > 40). This will be followed by a continuous infusion at 0.3 mg/kg/h for an additional 2 hours 50 minutes.

Patients in the control group will receive an equal volume of normal saline. The bolus loading dose will consist of normal saline 0.1 mL/kg administered intravenously over 10 minutes (or over 20 minutes if BMI > 40). This will be followed by a continuous infusion at 0.06 mL/kg/h for an additional 2 hours 50 minutes.

Study intervention dosing will be based on actual body weight.

Timing of study medication administration will be the same for both groups. For patients who are extubated in the operating room, the study medication will be initiated prior to leaving the operating room. For patients who remain intubated and transfer to the intensive care unit, the study medication will be administered based on the following criteria:

- If the patient is extubated before 07:00am on postoperative day 1, the study medication will be administered between 05:00am and 08:00am on postoperative day 1.
- If the patient is extubated after 07:00am on postoperative day 1 and before 07:00am on postoperative day 2, the study medication will be administered between 05:00am and 08:00am on postoperative day 2.
- If the patient is extubated after 07:00am on postoperative day 2 and before 07:00am on postoperative day 3, the study medication will be administered between 05:00am and 08:00am on postoperative day 3.
- If the patient remains intubated at 07:00am on postoperative day 3, the patient will be withdrawn from the study.

In the operating room, the study medication will be administered by the anesthesiology clinician (MD or certified registered nurse anesthetist). In the PACU or ICU, the study medication will be administered by the patient's bedside nurse.

Richmond Agitation and Sedation Scale (RASS) scores will be monitored per standard nursing protocols, as described in section 8.2. If the patient experiences sedation to a RASS score ≤ -2 , then the study medication will be halted and the procedures documented in section 7.1 will be followed.

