9.4.4 SAFETY ANALYSES

Psychotomimetic Symptoms:

The BPRS four-item positive symptom subscale score and the CADSS-6 score will be calculated for each patient. The distribution of scores will be assessed for normality using visual analysis of histograms and using the Kolmogorov-Smirnov test. If the scores are normally distributed, then the mean score in the two groups will be compared using a two-sample t-test. If the scores are not normally distributed, then the median score in the two groups will be compared using a Wilcoxon rank sum test.

Clinical and Adverse Events Checklist:

The number of patients reporting each side effect during the study medication infusion will be determined. The incidence of each side effect will be compared between the two groups using a chi-square test (or using a Fisher exact test in the case of rare side effects).

Significant Hypertension during Infusion:

The number of patients experiencing a systolic blood pressure > 180 mmHg during the study medication infusion or receiving an antihypertensive medication during the infusion that is not on the patient's home medication list will be determined. The incidence of significant hypertension will be compared between the two groups using a chi-square test.

Tachycardia during Infusion:

The number of patients experiencing a heart rate > 100 beats per minute during the study medication infusion will be determined. The incidence of tachycardia will be compared between the two groups using a chi-square test.

Nausea and Vomiting:

The number of patients reporting nausea and vomiting will be determined. The incidence of nausea and vomiting will be compared between the two groups using a chi-square test.

Other adverse events will be coded and reported as described in section 8.3.

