10.1.6 SAFETY OVERSIGHT

Safety oversight will be performed by an independent safety monitor (ISM). The ISM will be a physician with relevant expertise in the care of postoperative critically ill patients. The ISM will be independent from the study conduct and free of conflict of interest, or measures should be in place to minimize perceived conflict of interest. The ISM will review adverse events as they reported, according to the timelines outlined in section 8.3.5.

In addition to as-needed reviewing of reportable events, the ISM will review safety data every 6 months. This review will include the following safety outcomes described in section 8.2: psychotomimetic side effects, clinical and adverse events checklist, level of sedation, vital signs during study medication infusion, and nausea/vomiting.

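### Without an arterial catheter, Section 8.2 guarantees blood pressure only at least hourly and not at the end of the loading dose; one timed reading there would be a cheap improvement

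*Combined protocol and SAP*

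**What the plan says.** Section 8.2 places participants under ICU-standard monitoring during the infusion. Telemetry and pulse oximetry are continuous. Blood pressure is either "noninvasive blood pressure (at least hourly) or continuous invasive blood pressure (if an arterial catheter is present").

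One assessment is tied to the end of the load, and it concerns sedation: "The nurse will also be asked to perform one extra RASS assessment at the end of the 10-minute bolus loading dose".

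On dosing, Section 6.1.2 states that "the bolus loading dose will consist of ketamine 0.5 mg/kg administered intravenously over 10 minutes (or over 20 minutes if BMI > 40"), followed by 0.3 mg/kg/h for 2 hours 50 minutes. It also says who gives the drug when the infusion starts before the patient leaves theatre: "In the operating room, the study medication will be administered by the anesthesiology clinician (MD or certified registered nurse anesthetist").

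Section 8.2 defines the outcome: "Safety events will include significant hypertension during the infusion, defined as systolic blood pressure > 180 mmHg or the administration of an antihypertensive medication", where the drug must not be a home medication. Section 9.4.4 adds: "The incidence of significant hypertension will be compared between the two groups using a chi-square test". Under Section 10.1.6 the independent safety monitor reviews, every six months, "psychotomimetic side effects, clinical and adverse events checklist, level of sedation, vital signs during study medication infusion, and nausea/vomiting".

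**The concern.** The load is the fastest part of the dosing, and Section 2.3.3 itself links the risk of hypertension to how quickly the drug is given. Heart rate and oximetry are continuous. Cuff pressure is the vital sign that may have no value during or just after the load. The other structured safety instruments (BPRS subscale, CADSS-6, adverse events checklist) are given about 1 to 2 hours after the load begins, so they do not cover that moment either.

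The systolic part of the hypertension outcome can count only what is recorded. If ketamine caused a short rise above 180 mmHg around the end of the load, and it drew no new antihypertensive, a participant on cuff monitoring at the minimum frequency might be classed as event-free. Saline would not cause such a drug effect, so missed events of this kind would fall in the ketamine arm and pull the comparison toward no difference. The safety monitor would see the same incomplete record.

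**Working it through.** **1. Inputs.** Load 0.5 mg/kg over 10 min (20 min if BMI > 40), then 0.3 mg/kg/h for 170 min (6.1.2). Volume of distribution 2.4 L/kg, target level 225 ng/mL, distribution half-life about 10 min (4.3). Cuff pressure at least every 60 min without an arterial catheter (8.2). Target sample 32 (9.2).

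**2. The plan's own figure.** Section 4.3 computes the load as 2.4 × 0.225 = 0.54 mg/kg and rounds it to 0.5. This reproduces.

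**3. Rate of the load.**
- 10 min: 0.5 / (10/60) = 3.0 mg/kg/h, which is 3.0 / 0.3 = 10 times the maintenance rate.
- 20 min: 0.5 / (20/60) = 1.5 mg/kg/h, which is 5 times maintenance.
- Total dose: 0.5 + 0.3 × (170/60) = 1.35 mg/kg. The load is 0.5 / 1.35 = 37% of it, given in 10/180 = 6% of the time (20/190 = 11% if BMI > 40).

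A load is faster than maintenance by definition. These ratios show where the fast phase lies; they say nothing about blood pressure.

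**4. Guaranteed readings.** Infusion length is 10 + 170 = 180 min, or 190 min if BMI > 40. An hourly floor gives 3 cuff readings in either case, none of them fixed to the end of the load.

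**5. Illustration of capture.** Assume no arterial catheter and reading times unrelated to the start of the infusion. A rise lasting D minutes contains at least one reading, at interval T, with probability min(1, D/T):

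| Interval T | D = 10 | D = 20 | D = 30 | D = 60 |
|---|---|---|---|---|
| 60 min (floor) | 17% | 33% | 50% | 100% |
| 30 min | 33% | 67% | 100% | 100% |
| 15 min | 67% | 100% | 100% | 100% |

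The documents give none of the durations, neither of the shorter intervals, and no basis for random timing. The table shows how the answer depends on those unknowns. It does not estimate a miss rate.

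**6. Would a rise be short?** Two parts of Section 4.3 point different ways.
- Toward a sustained level: the regimen is meant to "quickly achieve the desired blood level of ketamine of 225 ng/mL and then maintain that level throughout the infusion". On the protocol's volume, ignoring elimination and slow distribution, the load gives 0.5 / 2.4 = 0.208 mg/L = 208 ng/mL, just under target. A rise driven by a steady level would persist, and hourly readings would find it.
- Toward a brief peak: the same section expects a higher peak before redistribution in patients with elevated BMI, and gives a distribution half-life about as long as the load. The context there is over-sedation, so this makes a short pressure peak plausible but does not establish one.

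**7. After the change.** The guaranteed minimum rises from 3 readings to 4, and one of them falls at the end of the load by design.

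**The case against.** The case for leaving the plan alone is substantial. Hourly is a floor, and practice may be denser. Infusions started in the operating room are run by an anesthesiology clinician, the documents give no pressure interval for that setting, and the hourly model has no stated basis there. Section 2.3.1 says that these doses have not been associated with clinically significant pressure changes, Section 2.3.3 says that the regimen avoids rapid boluses, and Section 5.2 excludes patients for whom a pressure rise is a serious hazard. New antihypertensive use counts as an event without any reading above 180 mmHg. In a trial of 32 with descriptive primary endpoints, one more reading is unlikely to change a chi-square result. Nor does the plan require a reading just before the infusion, so a single high value soon after extubation could not be attributed to the load in an individual.

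Most of this stands, and it is why the change is optional. Two parts are weaker. The reassurance in Section 2.3.1 cites a study whose title in the reference list describes a 96-hour infusion with co-administered clonidine. Clonidine lowers blood pressure (general pharmacology, not stated in the protocol) and is not part of this regimen, so that study says little about a 10-minute load after surgery. The attribution problem applies to individuals; randomization and identical timing still allow a comparison between groups.

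A reader might infer from the 17% that about 83% of load-related hypertension will be missed, or that monitoring is unsafe. The documents support neither. The 17% applies only to a rise that occurs, lasts 10 minutes, is untreated, and falls in a patient without an arterial catheter who is read at the bare minimum frequency. No probability for any of these is given.

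**Conclusion.** The gap in what the text guarantees is real: without an arterial catheter, no blood-pressure reading is required at the end of the loading dose, although systolic pressure above 180 mmHg during the infusion is a named safety event compared between arms. It is an opportunity for a cheap improvement, not an error or an internal contradiction.

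Its practical size cannot be estimated. It depends on whether short, untreated rises occur, on the actual cuff interval in the ICU, recovery unit and operating room, and on the share of participants with arterial catheters. The documents give none of these. If rises are sustained, or readings are frequent in practice, the loss is nil. The point touches one safety outcome and the safety monitor's review of it; no primary endpoint, dose or stopping rule is involved.

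**What to change.** In Section 8.2, add a sentence along these lines: *In both arms, for participants without continuous arterial pressure monitoring, whoever is administering the study medication will record one time-stamped blood-pressure reading at the end of the bolus loading dose (10 minutes, or 20 minutes if BMI > 40).* Naming the person who gives the drug covers operating-room starts as well as the bedside nurse.

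Reword the extra RASS in Section 8.2 so that it falls at the end of the bolus loading dose, without fixing it to 10 minutes. The two checks then coincide for participants with BMI > 40 as well.

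In Section 9.4.4, state that this reading counts in the hypertension analysis. It should be entered in the electronic health record, from which the research team already retrieves vital signs.

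The cost is one extra cuff reading per participant without an arterial catheter, at most 32 if nobody has one, plus two short edits in 8.2 and a note in 9.4.4. It needs no extra staff. Because both arms are read at the same time, ascertainment stays equal and the blind is unaffected.

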9.4 STATISTICAL ANALYSES

9.4.1 GENERAL APPROACH

For descriptive statistics, categorical data will be presented using frequency counts and percentages, normally distributed continuous data will be presented using means and standard deviations, and non-normally distributed continuous data will be presented using medians and interquartile ranges.

Normality will be assessed using visual analysis of histograms and using the Kolmogorov-Smirnov test. All inferential tests will be two-tailed, and p-values < 0.05 will be considered statistically significant.

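### Tachycardia is counted whatever the heart rate was before the infusion, and three safety events are summarised without an effect estimate or interval

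*Combined protocol and SAP*

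**What the plan says.** Section 8.2 sets the event: "Another safety event will be tachycardia, defined as heart rate > 100 beats per minute, during the infusion". Section 9.4.4 carries it into the analysis unchanged: "The number of patients experiencing a heart rate > 100 beats per minute during the study medication infusion will be determined", and then "The incidence of tachycardia will be compared between the two groups using a chi-square test". Neither section refers to a pre-infusion value, a change from baseline or new onset. Section 8.2 describes vital-sign monitoring for the infusion period only, and the baseline variables in 9.4.5 include no vital signs.

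The neighbouring events are handled in the same way: "The incidence of significant hypertension will be compared between the two groups using a chi-square test" and "The incidence of nausea and vomiting will be compared between the two groups using a chi-square test". For the Clinical and Adverse Events Checklist, the same section adds an alternative to chi-square: "or using a Fisher exact test in the case of rare side effects". The other three events have no such alternative.

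Section 9.4.1 supplies the rest: "categorical data will be presented using frequency counts and percentages", and "All inferential tests will be two-tailed, and p-values < 0.05 will be considered statistically significant". Section 9.4.2 plans confidence intervals for the feasibility proportions. None is planned for a safety event.

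**The concern.** Study drug starts either before the patient leaves the operating room or, for patients who stay intubated, on postoperative days 1 to 3 (6.1.2). Some of these patients may already have a heart rate above 100 for reasons unrelated to the drug. Under the present rule they are events in whichever arm they fall. They add equally to both arms in expectation and so dilute any difference the drug makes.

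Other parts of the protocol do allow for a prior state. The hypertension definition in 8.2 disregards antihypertensives that the patient takes at home, and 8.3.4 treats conditions present at screening as baseline. The second rule governs adverse event reporting and would not capture a heart rate that rose after surgery.

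The second gap is in the summary. Section 2.3.1 names hypertension and tachycardia as known risks of ketamine, and this trial is meant to inform a full-scale one. With about 16 patients per arm, a p-value does not show how large a harm the data leave open. An interval does.

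**Working it through.** **Inputs from the documents.** N = 32 (9.2); 1:1 allocation in blocks of 4 (6.3), hence 16 per arm; two-sided 0.05 (9.4.1). Section 7.2 lets randomized but untreated patients be replaced, and 9.3 names no safety population, so the safety denominators may not be exactly 16.

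**The plan's own figure.** No event rate, power or precision is stated for any safety comparison. The basis for N = 32 reproduces: 1.96 × √(0.25 × 0.75 / 32) = 0.150, the stated ±15%.

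**Assumptions (not in the documents).** New-onset risk of 35% on ketamine and 5% on placebo. Share above 100 before the infusion b = 20% or 30%, equal in both arms, and all of these patients still above 100 during it.

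**Step 1, dilution.** Counted rate per arm = b + (1 − b) × new-onset rate. The b terms cancel in the difference, so counted difference = (1 − b) × new-onset difference.

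| b | Ketamine | Placebo | Difference |
|---|---|---|---|
| 0 | 0.35 | 0.05 | 30 points |
| 20% | 0.20 + 0.80 × 0.35 = 0.48 | 0.20 + 0.80 × 0.05 = 0.24 | 24 points |
| 30% | 0.30 + 0.70 × 0.35 = 0.545 | 0.30 + 0.70 × 0.05 = 0.335 | 21 points |

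Other rates give the same factor. For 40% against 10%, the difference falls from 30 points to 27, 24, 21 and 15 at b = 10%, 20%, 30% and 50%.

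**Step 2, sensitivity, like for like.** Power by exact enumeration of all outcome tables. The new-onset set has about 16 × 0.80 ≈ 13 or 16 × 0.70 ≈ 11 patients per arm.

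| b | Test | Any tachycardia, 16 per arm | New onset, 13 or 11 per arm |
|---|---|---|---|
| 20% | Fisher | 17% | 31% |
| 30% | Fisher | 13% | 21% |
| 20% | Pearson chi-square | 30% | 49% |
| 30% | Pearson chi-square | 23% | 38% |

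If the number at risk varies binomially instead of being fixed at 13 or 11, the Fisher figures for new onset are 36% and 28%. At b = 20% about 13 × (0.35 + 0.05) = 5.2 events are expected in total, or 2.6 per arm, so a Fisher fallback would very likely apply. The Fisher rows are therefore the relevant ones.

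**Step 3, size of the tests.** The uncorrected chi-square at 16 per arm has a maximum type I error of 5.8% over all event rates. At 13 per arm the maximum is 7.6%, near an event rate of 50%.

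**Step 4, small counts.** With 16 per arm, each arm's expected number of events is half the total, so fewer than 10 events in all puts an expected cell below 5. The choice of test can then change the label: 4/16 against 0/16 gives chi-square p = 0.033 and Fisher p = 0.101.

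**Step 5, what an interval would show.** For 0/16, the exact two-sided 95% upper limit is 1 − 0.025^(1/16) = 0.206, or 21%. Newcombe 95% intervals for the risk difference: 6 against 2 events gives 0.25 (−0.05 to 0.51); 4 against 1 gives 0.19 (−0.08 to 0.44).

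**The case against.** The strongest reply is that the dilution is hypothetical. The documents give no pre-infusion tachycardia rate, and persistence into the infusion and a 30-point effect are assumed. Section 2.3.1 says doses this low have not been associated with clinically significant heart-rate changes. This stands as a limit on size. It does not affect the direction, which follows once any patient is above 100 beforehand and stays there.

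A new-onset count also has costs. It drops the patient whose existing tachycardia worsens, whom the present rule does count. For patients extubated in the operating room, the last reading before the drug falls around emergence and may be unstable. This stands, and it is why new onset should be shown beside the current count and not replace it.

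A reader might infer that only a p-value will be reported. The documents do not support that: 9.4.1 and 9.4.4 provide counts and percentages, from which a reader could derive an interval. A reader might also infer that a null result will be taken as proof of safety. No such plan is stated, the primary endpoints are feasibility measures, and the independent safety monitor reviews infusion vital signs and nausea/vomiting every 6 months (10.1.6). What remains is that the plan does not commit to an estimate or an interval.

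**Conclusion.** The point holds as a minor improvement to a secondary part of a feasibility trial. As written, the tachycardia rule multiplies any drug-related risk difference by (1 − b): 30 points become 24 at b = 20% and 21 at b = 30%, under the assumptions above. Three safety events have no planned effect estimate or interval, although at this size even zero events in an arm leaves rates up to 21% open.

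Three stronger readings are tempting and are not supported.

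- The tachycardia comparison is not biased under the null. Randomization balances pre-existing tachycardia in expectation, so the loss is in sensitivity and there are no extra false positives.
- The chi-square test is not seriously inflated at 16 per arm (at most 5.8%). The missing Fisher fallback is an inconsistency between adjacent paragraphs and no more.
- The rise in chi-square power to 49% or 38% is not what the new-onset count would deliver. With the Fisher fallback the figures are about 31% and 21%, against 17% and 13% for Fisher on the current count. That gain is real but modest, and power stays low either way, which is a further reason to rely on estimates and intervals.

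**What to change.** In 9.4.4:

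- Keep the count of any heart rate above 100 during the infusion. Beside it, report new-onset tachycardia among patients whose last pre-infusion heart rate was 100 or below, with the number at risk in each arm.
- For hypertension, tachycardia and nausea/vomiting, make per-arm counts and the risk difference with a 95% CI (for example Newcombe) the main summary.
- If a test is kept for these events, apply the Fisher fallback already given for the checklist.

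In 8.2, add the last pre-infusion heart rate to the vital signs retrieved from the electronic record.

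The cost is one more value per patient from a source already being searched, and a few lines of text. The downsides are a smaller new-onset set, its blindness to worsening of existing tachycardia (hence both counts), a reference reading that may be unstable around emergence, and the conservatism of Fisher's test. No clinical rule changes.
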